Throughout all phases of the study, most potassium values will be measured at fasting before taking ZS. Nothing should be taken by mouth except water, coffee or tea, with or without milk and/or sugar, and essential medications, for a minimum of 8 hours prior to the blood collection. Potassium level should be determined by both i-STAT and the Central Laboratory on all occasions. Treatment decisions (eg, dose titration, stopping rules) will be made based on

i-STAT potassium values, as these provide clinical sites with a real-time measurement, according to dose modification rules. Statistical analyses on the study data will in principle be based on S-K values as measured by the Central Laboratory.

Safety and tolerability will be assessed on an ongoing basis. Standard study assessments including blood potassium, clinical chemistry (including calcium, magnesium, sodium, phosphate, creatinine, bicarbonate, and blood urea nitrogen [BUN]), aldosterone, renin and hematology parameters, urinalysis, vital signs, physical examinations, and electrocardiograms (ECGs) will be assessed. All women of childbearing potential will have a urine pregnancy test prior to enrollment and at their End of Study (EOS) visit.

Stopping rules will be implemented to ensure subjects discontinue the study treatment and receive alternative therapy in case of significant hyperkalemia, hypokalemia, arrhythmias, or development of congestive heart failure or end stage renal failure.

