1.3 Number of subjects

Sample size of in total 150 subjects to be enrolled to this study was determined so that at least safety data of 100 subjects treated by ZS as long as one year will be collected, assuming 35% drop out rate.

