2.1.2 Full analysis sets

All efficacy analyses will be performed using an Intent-to-Treat (ITT) principle based on the full analysis sets.

FAS-CP : For the correction phase (CP), the full analysis set will include all patients that receive at least one dose of ZS during the correction phase and have any post-baseline correction phase S-K values.

FAS-MP : For the subsequent long-term maintenance phase (MP), the full analysis set will include all patients who receive at least one dose of ZS during maintenance phase and have any post-baseline maintenance phase S-K values.

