4.1.3 Visit/Time windows

In principle, analyses will be based on **nominal visit basis**, only if scheduled visit is available. In absence of scheduled visit, the unscheduled visits and discontinuation visit will be mapped according to the below windows and utilized for by-visit analysis (Table 2 and Table 3).

If scheduled visit is missing,

- If an unscheduled visit exists for that visit window, it will be used.
- If two or more unscheduled visits are available for the same window, the one closest to nominal target day will be used.

- If two unscheduled observations are equally close to target day, the last observation will be used.

As outlined in the table, S-K measurement taken within 1 day (2 days on QOD regimen) after last dose will be regarded as on-treatment and used in analysis. Unscheduled S-K measurement taken more than 1 day (2 days on QOD regimen) after last dose of ZS could be mapped to EOS (Follow up) visit.

Table 2 Visit window for correction phase

Study Visit	Nominal Day	Target Day	From	To
1	Screening (CP Baseline)		-	-1
2	CP Day 1 (CP Baseline)	1	1	1
3	CP Day 2	2	2	2
4	CP Day 3	3	3	3
5	CP Day 4	4	4	4
EOS	CP Follow Up	10	5	17

Table 3 Visit window for maintenance phase

Study Visit	Nominal Day	Target Day	From	To*
6	MP Day 1 (MP Baseline)	1	1	1
7	MP Day 2	2	2	3
8	MP Day 5	5	4	8
9	MP Day 12	12	9	15
10	MP Day 19	19	16	22
11	MP Day 26	26	23	39
12	MP Day 54	54	40	67
13	MP Day 82	82	68	95
14	MP Day 110	110	96	123
15	MP Day 138	138	124	151
16	MP Day 166	166	152	179
17	MP Day 194	194	180	207
18	MP Day 222	222	208	235
19	MP Day 250	250	236	263
20	MP Day 278	278	264	291

Study Visit	Nominal Day	Target Day	From	To*
21	MP Day 306	306	292	319
22	MP Day 334	334	320	347
23	MP Day 362	362	348	Last dose + 1 day (2 days, on QOD regimen)
EOS	MP Follow Up	last dose + 7 days	last dose +2 days (+3 days, on QOD regimen)	last dose + 14 days

*S-K measurements more than 1 day (2 days, on QOD regimen) after last dose will be regarded off-treatment and will be mapped to the EOS visit.

Note : Any available measurements regardless of scheduled or unscheduled will be taken into account when summarizing the incidence of certain event based on most extreme (lowest or highest) values in safety evaluation (e.g. analysis of incidence of hypokalemia, etc).

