4.1.5 Handling of drop outs and missing data

4.1.5.1 Missing central lab individual measurements of S-K

In the event of missing S-K data from the central laboratory, the i-STAT data will be used to replace missing data by adjusting for the average paired difference between the central and i-STAT levels collected at the same visit. As illustration of the change methodology, if the mean difference between central laboratory and i-STAT assessments for all patients with both values available at the relevant visit is 0.12 mmol/L higher for the central laboratory assessment, then 0.12 mmol/L will be added to the i-STAT level to impute the missing central laboratory assessment.

The above imputation procedure for missing central lab S-K based on non-missing i-STAT level will be carried out separately for samples tested on or before 3rd-December-2017 and for samples tested on or after 4th-December-2017.

If both central lab S-K and i-STAT are missing, the measurement at that visit/timepoint will be left as missing.

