4.2.4 Efficacy

4.2.4.1 Efficacy in the Maintenance Phase

Analysis of S-K related variables

- Proportion of patients who can maintain normokalemia (defined as S-K level of ≥ 3.5 and ≤ 5.0 mmol/L, inclusive) on ZS at each Maintenance Phase study visit

Number (%) of subjects who can maintain normokalemia at each Maintenance Phase study visit and last on treatment visit will be tabulated with binomial proportion and its 95%CI.

- Proportions of patients who were hypokalemic (< 3.5 mmol/L) or hyperkalemic (> 5.0 mmol/L) at each Maintenance Phase visit.

For each visit and last on treatment, patients will be classified to either normokalemic, hypokalemic or hyperkalemic by their S-K value. Number and proportion for each category will be tabulated.

- Observed values at visit and change from baseline in S-K over time

Observed S-K values at each visit/last on treatment and changes from CP baseline and from MP baseline will be summarized by descriptive summary statistics. For changes from baseline, 95%CI will be also presented.

- Subject-level average S-K over certain period of time
- Proportion of patients with average S-K ≤ 5.1 mmol/L
- Proportion of patients with average S-K ≤ 5.5 mmol/L

Average S-K level per subject will be calculated over the certain period of time (as specified in section 3.2.1). Continuous summary statistics will be provided for each. In addition, number (%) of subjects meeting ≤ 5.1 or ≤ 5.5 mmol/L will also be summarized with binomial proportion and its 95%CI.

- Model-based estimates for S-K over time as well as average S-K levels over certain period of time

The log-transformed S-K data will be analysed with mixed model as described in section 4.1.9. All post-baseline data will be included into the model. The LS Mean and 95% CI at each timepoint as well as over certain period of time (as specified in section 3.2.1) will be produced using appropriate contrasts. The estimates and 95% CIs will be back-transformed to original scale and tabulated.

- Number of normokalemic days during Maintenance Phase

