The number of normokalemic days during the MP will be calculated assuming that the time interval between assessments is normokalemic only if both the beginning and end assessments for that time interval display normal S-K values. If an intermediate scheduled assessment time point is missing, then the scheduled assessment is regarded as not normokalemic. In order to determine this variable all scheduled or unscheduled fasting S-K will be taken into calculation. Descriptive statistics and 95% CI for mean for the number of normokalemic days will be provided.

- Change in S-K level from the last on-treatment Maintenance Phase visit to the End of Study

To investigate if S-K increases after stopping treatment, change in S-K from last on-treatment visit to MP EOS (MP follow up) visit will be summarized with continuous summary statistics and 95% CI for mean.

Sensitivity analysis for missing S-K values

For the mean S-K over time, longitudinal repeated measures model specified above will serve as a sensitivity check to missing S-K values. It provides estimates of S-K over time *had subjects remained on ZS for planned 52 weeks* under the Missing At Random assumption.

Further sensitivity analyses may be conducted depending on the volume of missing data as well as on the reason of study discontinuation.

Sensitivity analysis with iSTAT potassium measurements

Since the ZS dose adjustment during study is based on iSTAT measurement, analyses with categorized values (e.g. proportion of subjects with normokalemia) are expected to be sensitive to which of S-K or iSTAT K are analysed.

Summary of Potassium value over time, proportion of subjects with normokalemia and number of normokalemic days will be repeated using iSTAT potassium measurements instead of S-K values provided by Central lab. Only observed iSTAT values measured within last ZS dose + 1 day (+ 2 days on QOD regimen) will be used.

Sensitivity analysis with iSTAT potassium measurements for Correction Phase will be also carried out as outlined in section 4.2.5

Analysis with S-K adjusted for assay change bias

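### By-visit normokalemia proportions are in effect on-treatment, observed-case figures: this does not fit the stated ITT principle and can overstate late maintenance in the full FAS-MP

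*SAP*

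**What the plan says.** Section 2.1.2 sets the principle: "All efficacy analyses will be performed using an Intent-to-Treat (ITT) principle based on the full analysis sets". For the Maintenance Phase, "the full analysis set will include all patients who receive at least one dose of ZS during maintenance phase", provided that they also have a post-baseline S-K value in that phase.

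The operational rules are narrower:

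- **4.1.3, Table 3 footnote:** "S-K measurements more than 1 day (2 days, on QOD regimen) after last dose will be regarded off-treatment". Such values go to the EOS visit.
- **4.1.5.1:** a missing central value is replaced by an adjusted i-STAT value. If both are absent, "the measurement at that visit/timepoint will be left as missing".
- **4.1.5.2:** after early discontinuation, the last assessment is placed in its own window. Nothing is assigned to later visits.
- **4.2.4.1:** "For each visit and last on treatment, patients will be classified to either normokalemic, hypokalemic or hyperkalemic by their S-K value". No denominator is stated.

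Section 1.2 adds: "Stopping rules will be implemented to ensure subjects discontinue the study treatment and receive alternative therapy in case of significant hyperkalemia". It names hypokalemia as well. Table 1 gives the i-STAT limits: dosing stops at 2.9 or below and above 6.5 at any dose, and at 3.0-3.4 on the lowest regimen.

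The only missing-data check specified in 4.2.4.1 is the mixed model for mean S-K, under Missing At Random. Further sensitivity analyses are optional and not described.

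**The concern.** The first secondary objective concerns the proportion of ZS-treated subjects in whom normokalemia can be maintained over prolonged periods. A subject who stopped on Day 100 has no on-treatment value at Day 362 and cannot be placed in any of the three categories there. The Visit 23 percentage then describes those still taking drug.

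This would matter less if leaving were unrelated to potassium. Table 1 makes it partly related: some subjects leave because their potassium was out of range. Their failure counts at the visit where it occurred, if the value falls inside the on-treatment window, and then disappears from all later rows. A reader who takes the ITT statement at face value would read the late-visit percentage as a rate for the whole FAS-MP. No planned analysis of the proportions would show how far the two differ.

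**Working it through.** **Step 1. The plan's own figure.** Section 1.3 enrols 150 so that "at least safety data of 100 subjects treated by ZS as long as one year will be collected, assuming 35% drop out rate". Inflating 100 for 35% loss gives 100 / (1 - 0.35) = 153.8, or 154. Conversely, 150 x 0.65 = 97.5. Both are close to the stated 150 and 100, so the planning assumption is reproduced approximately. About 98 subjects remain at Day 362 and 150 - 98 = 52 have dropped out.

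**Step 2. Assumptions that the SAP does not supply.**

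- Observed normokalemia at Day 362: 78/98 = 79.6% (exact 95% CI 70.3-87.1%).
- Share f of drop-outs that are potassium failures: 10%, 25%, 50%, and 100% as the extreme.
- FAS-MP of about 150. This is an approximation, because 150 is the number enrolled, which 2.1.1 defines by signed consent.

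**Step 3. Count potassium failures as not normokalemic.** Let k = f x 52, rounded. Column A adds only these k subjects to the denominator: 78 / (98 + k). Column B keeps all 150 and gives the other drop-outs the observed rate: [78 + (1 - f) x 52 x 78/98] / 150.

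| f | k | A | B |
|---|---|---|---|
| 10% | 5 | 78/103 = 75.7% | 76.8% |
| 25% | 13 | 78/111 = 70.3% | 72.7% |
| 50% | 26 | 78/124 = 62.9% | 65.8% |
| 100% | 52 | 78/150 = 52.0% | 52.0% |

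The exact 95% CI for 78/150 is 43.7-60.2%. In column A the drop from 79.6% is about 4, 9 and 17 points, with a bound of about 28. If f = 0, both formulas return 79.6% and there is no gap.

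**Step 4. Other observed rates (column A).** An observed 59/98 = 60.2% becomes 59/103 = 57.3% at f = 10% and 59/150 = 39.3% at the bound. An observed 88/98 = 89.8% becomes 88/103 = 85.4% and 88/150 = 58.7%.

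**Step 5. Effect of the denominator.** If part of the 35% is lost before the Maintenance Phase, the bound shrinks. With an illustrative FAS-MP of 130 and the same 98 remaining, it is 78/130 = 60.0%.

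**The case against.** The strongest reply is that the outcome is on-treatment by its own wording: 3.2.1 defines it for patients on ZS at each visit, and 4.1.3 and 4.1.4 set out the on-treatment window openly. This stands in part. An on-treatment row is a legitimate display of that outcome, so one cannot say that the row should not be shown. But then the ITT sentence in 2.1.2, which covers all efficacy analyses, is the wrong label.

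The observed-case denominator is also an inference, since none is stated. Three categories defined by a value, with no place for a subject without one, make it the natural reading. If something else was meant, the SAP needs to say so.

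The last on-treatment row keeps subjects who stopped, and disposition is tabulated by reason to Visits 17 and 23 (4.2.1.1). Both help. However, that row pools early and Day 362 values and gives no 12-month rate, and the disposition table does not change the percentages.

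A reader might infer three stronger points that the documents do not support:

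- **That the stopping rules remove potassium failures generally.** Under Table 1, i-STAT 5.1-6.5 leads to titration, or to no change on 15 g QD, and 3.0-3.4 leads to titration on all but the lowest regimen. These subjects stay in.
- **That the whole-phase average S-K proportions (5.1 or below, 5.5 or below) share the bias.** FAS-MP membership requires a post-baseline value, so early stoppers generally enter the Day 2 to Day 362 average and carry their extreme values into it.
- **That missing data are handled in opposite ways.** For normokalemic days, "If an intermediate scheduled assessment time point is missing, then the scheduled assessment is regarded as not normokalemic". That rule concerns intermediate visits, not time after discontinuation, so the contrast is weak.

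**Conclusion.** The point holds in a limited form. The by-visit normokalemia proportions are in effect on-treatment, observed-case estimates, and the ITT label does not fit them. As rates for all FAS-MP subjects, the late-visit figures are too high whenever any drop-out is potassium-related, assuming that such a subject counts as not maintained and that the other drop-outs do no better than those still observed.

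The size is not known, because the SAP gives no share of drop-outs due to potassium. With the planned 35% loss and an assumed 80% observed, a share of 10% to 50% implies an overstatement of about 4 to 17 points. It would be tempting to quote 28 points as the bias, but that figure treats every drop-out as a failure and uses enrolled subjects as the FAS-MP. It is only a worst-case bound.

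This should be fixed before analysis, but it does not threaten the study's main purpose. The primary objective is safety, and 4.1.1 declares all analyses descriptive.

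**What to change.** 1. In 2.1.2 and 4.2.4.1, label the by-visit S-K rows as on-treatment, observed-case estimates and state their denominator.
2. Show the number on treatment at each visit.
3. For by-visit normokalemia, pre-specify two FAS-MP-based companion rows beside the on-treatment row. The first counts potassium-related discontinuations as not normokalemic at every later visit. The SAP should define such a discontinuation (for example, a Table 1 stop) and say how other drop-outs enter the row, since columns A and B above differ by about 1 to 3 points. The second, labelled as a bound, counts all discontinued or missing subjects as not normokalemic.
4. Leave the whole-phase average S-K proportions unchanged.

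The cost is SAP wording, the n at each visit, the companion rows in the by-visit normokalemia tables, and a companion figure less favourable than the on-treatment one. No new data are needed.

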1.2 Study design

The study is an open label, single arm study with flexible dose regimen focused on assessing long-term safety and tolerability of ZS in Japanese subjects with hyperkalemia.

Correction Phase: If the subject is normokalemic (i-STAT [A portable blood analyser] potassium between 3.5 and 5.0 mmol/L, inclusive) on the morning of Correction Phase Study Day 2 after 3 doses of ZS 10 g, they will enter the Maintenance Phase. If the subject is not normokalemic, they will receive an additional 24 hours of ZS 10 g TID treatment (6 total doses). If the subject's i-STAT potassium value is between 3.5 and 5.0 mmol/L, inclusive, on the morning of Correction Phase Study Day 3, the subject will enter the Maintenance Phase. If the subject is not normokalemic, they will receive an additional 24 hours of ZS 10 g TID

treatment (9 total doses). If the subject's i-STAT potassium value is between 3.5 and 5.0 mmol/L, inclusive, on the morning of Correction Phase Study Day 4, the subject will enter the Maintenance Phase. If the i-STAT potassium value is still < 3.5 mmol/L or ≥ 5.1 mmol/L on the morning of Correction Phase Study Day 4, after 72 hours of TID treatment, the subject will be withdrawn from the study and referred to their normal health care provider for standard of care treatment. Subjects withdrawn from the Correction Phase of the study will return to the clinic 7 (± 1) days after their last dose of ZS for an End of Study (EOS) visit.

Maintenance Phase: Patients will initially be dosed with ZS at a starting dose of 5g QD. During the Maintenance Phase, the ZS dose may be increased up to 15 g QD or decreased down to 5g QOD (or 2.5 g QD) based on i-STAT potassium measurements as outlined in [Table 1](#).

Table 1 Dose Adjustment during MP

Current dose	i-STAT Potassium Value (mmol/L)	Dose Adjustment
5g QOD or 2.5 g QD	≤ 2.9	Discontinue dosing
	3.0-3.4	Discontinue dosing
	3.5-5.0	No change
	5.1-6.5	5g QD
	>6.5	Discontinue dosing
5g QD	≤ 2.9	Discontinue dosing
	3.0-3.4	5g QOD or 2.5 g QD
	3.5-5.0	No change
	5.1-6.5	10g QD
	>6.5	Discontinue dosing
10g QD	≤ 2.9	Discontinue dosing
	3.0-3.4	5g QD
	3.5-5.0	No change
	5.1-6.5	15g QD
	>6.5	Discontinue dosing
15g QD	≤ 2.9	Discontinue dosing
	3.0-3.4	10g QD
	3.5-6.5	No change
	>6.5	Discontinue dosing

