2.2 Protocol deviations

Protocol deviations will be identified programmatically or manually prior to database lock. Subjects who deviate from important protocol conditions (e.g. selected inclusion/exclusion criteria) will be reported as having important protocol deviations.

Important protocol deviations would include but not limited to:

- Patients who received ZS but did not meet Inclusion/Exclusion criteria
- Patients who received prohibited concomitant medication or non-drug therapy
- Patients who received wrong ZS dose regimen (including incorrect up-/down-titration)
- Study drug compliance < 80% or > 120%.

No protocol deviations will lead to exclude subjects from analysis. All the efficacy analyses will be based on the FAS and all the safety analyses will be based on SAF for each phase.

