4.2 Analysis methods

4.2.1 Study patients

4.2.1.1 Disposition of patients

The disposition of subjects for the enrollment period, correction phase treatment period, the maintenance phase treatment period and follow-up period will be summarized.

The summary of disposition for the enrolment period will include all Enrolled subjects (who signed informed consent).

The summary of disposition for correction phase will include SAF-CP. This summary will include subjects completing and discontinuing the correction phase treatment period.

The summary of disposition in the maintenance phase treatment will include SAF-MP. This summary will include subjects completing and discontinuing the maintenance treatment

period up-to Visit 17 (MP Day 194) and up-to Visit 23 (MP Day 362), broken down by reasons for discontinuation.

The summary of disposition in CP follow up period will include all subjects who discontinued correction phase or completed correction phase but did not enter MP. The summary of disposition in MP follow up period will include all subjects who discontinued or completed MP. For each, summary will include subjects completing and discontinuing the follow up period, broken down by reason for discontinuation.

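### The mean S-K change after stopping ZS pools completers with subjects stopped for extreme potassium, so its size cannot be put down to withdrawal alone

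*SAP*

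**What the plan says.** Under SAP 4.2.4.1 this variable has a stated purpose: "To investigate if S-K increases after stopping treatment, change in S-K from last on-treatment visit to MP EOS (MP follow up) visit will be summarized". The output is one summary "with continuous summary statistics and 95% CI for mean". No split by reason for stopping is specified.

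The population is FAS-MP. Section 2.1.2 says "the full analysis set will include all patients who receive at least one dose of ZS during maintenance phase", provided they also have a post-baseline S-K value. Section 2.2 adds "No protocol deviations will lead to exclude subjects from analysis". Section 4.2.1.1 shows that follow-up covers both kinds of subject: "The summary of disposition in MP follow up period will include all subjects who discontinued or completed MP".

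In section 1.2, Table 1 gives the instruction "Discontinue dosing" for i-STAT potassium of 2.9 mmol/L or below, or above 6.5, at every dose level, and for 3.0-3.4 at the lowest level. The same section says: "Stopping rules will be implemented to ensure subjects discontinue the study treatment and receive alternative therapy in case of significant hyperkalemia, hypokalemia".

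Section 4.1.4 defines the start value as the last measurement within 1 day of the last dose (2 days on QOD), scheduled or not. The end value is the EOS visit. Table 3 places it between 2 days (3 on QOD) and 14 days after the last dose, with a target of 7 days. Section 4.1.3 adds: "Unscheduled S-K measurement taken more than 1 day (2 days on QOD regimen) after last dose of ZS could be mapped to EOS (Follow up)".

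**The concern.** The trial has a single arm. Among the efficacy variables in section 3.2.1, this is the only one that compares S-K on treatment with S-K off treatment, so it is where a reader will look to see whether potassium control depends on continued ZS.

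For a completer, treatment ends because the schedule ends, and the last on-treatment value is not selected for being high or low. For a subject stopped under Table 1, the start value can be the central-laboratory sample paired with the i-STAT reading that caused the stop. A value selected as extreme tends to be followed by a less extreme one whatever the drug does. Alternative therapy, if it starts before the EOS sample, moves potassium the same way: down after a hyperkalemia stop, up after a hypokalemia stop. Neither influence belongs to the question asked, and the planned 95% CI reflects neither. The reported rise could be too small or too large by an amount that depends on the mix of stopping reasons.

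**Working it through.** **1. The plan's own figure.** Section 1.3 enrols 150 so that at least 100 have one year of treatment, at 35% dropout. 100 / (1 - 0.35) = 153.8, so 154; conversely 150 x 0.65 = 97.5. This is close to the stated 150 and is not in dispute. It is useful here only as a bound: 150 x 0.35 = 52.5 dropouts from all causes. The SAP does not say how many would be potassium-rule stops.

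**2. The provisions side by side.**
- Population (2.1.2, 4.2.1.1): completers and early stoppers together.
- Start value (4.1.4): may be the sample taken when the stop was triggered.
- End value (4.1.3, Table 3): an off-treatment value up to 14 days after the last dose. No rule covers other potassium therapy given by then.
- Subgroups for S-K (4.2.4.1): none by completion or reason for stopping.
- Sensitivity analyses (4.2.4.1): reason for discontinuation appears only in an optional sentence under missing S-K values. The subjects at issue here have observed values.
- i-STAT repeat (4.2.4.1): restricted to on-treatment values, so it cannot inform this change.

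**3. Effect of hyperkalemia stops.** Let f be their share of analysed subjects.

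Pooled mean = (1 - f) x rise + f x change in stopped subjects.

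Assumed, not from the SAP: rise 0.4 mmol/L, change -1.0 mmol/L.

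| f | Calculation | Pooled mean |
|---|---|---|
| 2% | 0.98 x 0.4 - 0.02 x 1.0 | 0.37 |
| 5% | 0.95 x 0.4 - 0.05 x 1.0 | 0.33 |
| 10% | 0.90 x 0.4 - 0.10 x 1.0 | 0.26 |
| 20% | 0.80 x 0.4 - 0.20 x 1.0 | 0.12 |
| 35% | 0.65 x 0.4 - 0.35 x 1.0 | -0.09 |

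**4. When the direction is lost.** The pooled mean is zero at f = rise / (rise - change) = 0.4 / 1.4 = 29%. For rises of 0.2 to 0.6 and changes of -0.5 to -1.5, this point runs from 0.2 / 1.7 = 12% to 0.6 / 1.1 = 55%.

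**5. Effect of hypokalemia stops.** Assume no rise in other subjects and +1.0 in these. The pooled mean is then 0.05 at f = 5% and 0.10 at 10%. Part of that +1.0 may be a real withdrawal effect, so these figures are an upper limit on the bias for that assumed change.

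**6. Compared with sampling error.** With 100 subjects and an assumed SD of 0.5 to 0.7, the 95% half-width is about 1.96 x SD / 10 = 0.10 to 0.14. In step 3 the shift is 0.40 - 0.33 = 0.07 at f = 5% and 0.40 - 0.26 = 0.14 at f = 10%. The first lies within the half-width; the second is at or beyond it.

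**The case against.** The other side has a substantial case.

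- **The question is directional.** The plan asks whether S-K rises. At a small share of potassium stops the pooled mean still shows a rise, and the two kinds of stop partly offset each other. This stands. A reader might infer that the analysis cannot show a rise at all; the documents do not support that.
- **The counts are assumed.** A hyperkalemia stop needs i-STAT above 6.5; readings of 5.1-6.5 lead to a higher dose, or to no change at 15 g. Nothing in the SAP suggests that such stops are common. This stands.
- **Timing of alternative therapy.** Section 1.2 does not say that it starts before the EOS sample. That it may is an inference from the 14-day window.
- **Hypokalemia stops.** A rise after stopping a potassium-lowering drug may partly be the withdrawal effect sought. It would be wrong to call all of it bias.
- **Other planned outputs help.** Section 4.1.6 includes the median, which resists a small extreme group. Suppose 120 of 130 subjects have mean change 0.50 and SD 0.5, and 10 lie well below. The median is then the 55/120 quantile of the 120, about 0.45. With a fall of 1.2 in those 10, the mean is (120 x 0.5 - 10 x 1.2) / 130 = 0.37. Disposition by reason and the classification of last on-treatment S-K also show roughly what the mix is. None of these gives the change by reason for stopping, so they limit the problem without removing it.
- **Standing of the variable.** It is secondary, and section 4.1.1 makes all analyses descriptive. This limits the weight of the point.

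The use of unscheduled values as EOS values is marginal, since section 4.1.3 maps them only when the scheduled visit is missing.

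**Conclusion.** The point holds in a limited form. The pooled mean combines withdrawal of ZS with regression from a selected extreme and, possibly, with other treatment. Its size is therefore not attributable to withdrawal alone, and no other planned analysis separates the parts.

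Under the assumed rise of 0.4 and change of -1.0, the understatement is 0.07 mmol/L at 5% hyperkalemia stops and 0.14 at 10%. A reader might go further and expect the direction to reverse. In that example it takes about 29% of analysed subjects; if that share applied to all 150 it would be about 43 of the 52.5 dropouts planned for all causes. Only a small rise combined with a large fall brings the figure down to 12%. The SAP gives no rise, SD or count of potassium stops, so all these magnitudes are illustrative. This is a cheap improvement to a descriptive secondary analysis; it does not show that the analysis fails.

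**What to change.** In SAP 4.2.4.1, present the change from last on-treatment S-K to MP EOS in three rows, with the pooled FAS-MP figure alongside:

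- (a) subjects who completed MP treatment through Visit 23, named as the row that addresses the stated question;
- (b) subjects stopped under a potassium stopping rule;
- (c) subjects stopped for any other reason.

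Fix the assignment to rows before the data are reviewed. Section 4.2.1.1 already summarizes reasons for discontinuation; if those categories do not identify potassium-rule stops, the last i-STAT value and dose level can be set against Table 1.

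Do not exclude subjects because potassium therapy was started after the last dose. A rise in potassium is a likely reason for such therapy, so the exclusion would condition on the outcome and favour subjects who did not rise. Where the therapy is recorded, flag or count it in each row.

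The cost is one extra table split and smaller numbers per row. Row (a) describes completers only, which is why the other rows and the pooled figure stay. Section 8.1 leaves this variable out of the interim analysis, so only the final analysis is affected. No clinical rule changes.
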